### **Study Protocol and Statistical Analysis Plan**

Before the study, One Way ANOVA test with a significance level of 5% was used for the sample size calculation. Based on this analysis, the sample size was determined as at least 11 people in each group and a total of 44 subjects to detect a difference between groups. This cross-sectional study was approved by Ondokuz Mayıs University Clinical Research Ethics Committee (OMUKAEK) Samsun, Turkey (protocol number; 2019/324).

Fourty four individuals, 22 males and 22 females who were older than 18 were enrolled in the study. The study groups were selected according to the following criteria from individuals who applied to the Ondokuz Mayıs University Faculty of Dentistry Periodontology Department Clinic for treatment or control, accepted to participate in the study, were systemically healthy, did not take any medication in the previous 6 months, and did not receive periodontal treatment in the previous 6 months:

Group 1: (SP) Stage 3 Grade C patients (n:11)

Group 2: (P) Stage 3 Grade A patients (n:11)

Group 3: (SH) Periodontally healthy smokers (n:11)

Group 4: (H) Non-smokers with periodontally healthy (n:11)

Individuals were included as smokers if they had smoked  $\geq 10$  cigarettes/day for  $\geq 5$  years, whereas individuals were included as nonsmokers if they had no previous history of smoking. The periodontitis stage III patients were evaluated clinically and radiographically, and were selected to have teeth with CAL  $\geq 5$  mm in at least 30% of them. Exclusion criterias were as follows; patients under the age of 18, pregnant or lactating women, patients who have a history of with systemic disease or cancer or chemotherapy and radiotherapy or ongoing drug therapy who might be affect the clinical characteristics of periodontitis, patients who smoke less than 10 cigarettes/day or who quit smoking.

In order to standardize the study, all radiological and clinical examinations were performed by a single investigator. In clinical examination, Plaque Index (PI), Gingival Index (GI), bleeding on probing (BOP), probing depth (PD) and clinical attachment loss (CAL) scores were measured and recorded from 6 regions of each tooth (buccomesial, midbuccal,

buccodistal, linguo/palatomesial, midgingual/palatal, linguo/palatodistal regions) with using using millimetric (mm) calibrated University of North Carolina (UNC) (Hu-Friedy, Chicago, Illinois, USA). And up-to-date panoramic radiographs were taken from all patients on the day of the examination to determine periodontal status. After the clinical and radiographic evaluations, the participants were asked to come for GCF sample and treatment 1 day after the clinical evaluations, since bleeding may occur during probing.

From the patients in the SP and P groups, GCF samples were obtained from the 5 deepest pockets before the treatment, on the 15th and 30th days after the treatment. GCF samples were obtained taken from 5 randomly selected teeth with GI=0 PI=0 and SPD  $\leq 3$  from healthy individuals in the SH and H groups.

GCF samples were acquired by intrasulcular technique from selected pockets. Before sampling, the sites were isolated with cotton rolls, saliva and supragingival plaque were removed by cotton pellets, if present. Standardized filter paper strips (Peripaper® Oraflow Inc. New York, USA) were placed in the pocket for 30 seconds. Strips contaminated with blood or saliva were discarded. The absorbed GCF volume was measured with a precalibrated Periotron 8000 instrument (PeriotronR 8000, Pro Flow Inc., Amityville, NY, USA). Then, the strips were placed in sterile 0.5 ml Eppendorf (Eppendorf AG, Hamburg, Germany) tubes. Eppendorf tubes were stored at -80°C in Ondokuz Mayıs University Faculty of Medicine Department of Biochemistry until ELISA analysis. GCF samples were converted to an actual volume ( $\mu$ L) by reference to a standard curve.

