### **Statistical analysis**

SPSS for Windows Ver. for statistical analysis and graphics. 22.0 (SPSS Inc., Chicago, ILL, USA) and MS-Excel 2016 programs were used. Statistical significance level was accepted as p<0.05.

The normal distribution of the data in our study was evaluated with the Shapiro-Wilks test. The mean±standard deviation was used for the descriptive statistics for the normally distributed variables, and the median (min-max) value for the non-normally distributed variables. While examining the distribution of the gender variable in the groups, the result of the Chi-Square test was evaluated.

OneWay ANOVA test was applied to the variables showing normal distribution in the comparison of the data between groups. In post-hoc analyses, homogeneously distributed data according to Levene variance homogeneity test were evaluated with Tukey test, and data that were not homogeneously distributed were evaluated with Tamhane T2 test. Variables that did not show normal distribution were evaluated with the Kruskal-Wallis test. Bonferroni corrected Mann-Whitney U test was used in order to determine the group that caused the difference in the variables with a significant difference as a result of the Kruskal-Wallis test.

Paired-Sample T Test and Repeated Measured Analysis of Variance were used for the variables showing normal distribution in the evaluation of the within-group changes according to time. Significant differences as a result of analysis of variance were examined with Bonferroni, one of the multiple comparison tests. Variables that did not show normal distribution were analyzed with the Friedman test. The Wilcoxon test was used to determine the group that caused the difference in the variables with a significant difference as a result of the Friedman test.

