## **RESULTS**

### **Demographic Findings**

The distributions of gender and age of the groups were as follows: SP (seven male and four female subjects; mean age:  $40,9 \pm 9,28$  years); P (three male and eight female subjects; mean age:  $41 \pm 12,30$  years); SH (seven male and four female subjects; mean age:  $30,27 \pm 9,99$  years); H (three male and eight female subjects; mean age:  $26,36 \pm 4,20$  years).

The study groups were evaluated in terms of age and gender, and a significant difference was found between the groups in terms of mean age ( $\chi^2=16,567$ ; p=0.001). There was no

significant difference in terms of gender ( $\chi^2=0.364$ ;  $p=0.546$ ). The mean age of the H group was lower than the mean age of the patients in the SP ( $Z=18,000$ ;  $p=0.006$ ) and P groups ( $Z=16.682$ ;  $p=0.014$ ). It was determined that the mean age of the individuals was similar ( $Z=3,682$ ;  $p=1,000$ ) between group H and group SH.

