### **GCF IL-17E levels**

In the analysis of GCF IL-17E levels, there was no statistically significant difference between the groups in terms of both periodontal disease and smoking at any time ( $p>0.05$ ).

In the evaluation of the change with non-surgical periodontal treatment, there was no statistically significant change in GCF IL-17E levels at any time in both the SP group and the P group ( $p>0.05$ ).

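### The plan asks for no between-group estimate or confidence interval, so null results with 11 per group cannot be interpreted, and the healthy groups are called similar in age without support

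*Combined protocol and SAP*

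**What the plan says.** The opening section states that "One Way ANOVA test with a significance level of 5% was used for the sample size calculation" and concludes that the study needs "at least 11 people in each group and a total of 44 subjects to detect a difference between groups". It gives no endpoint, effect size, SD or power.

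The Statistical analysis section sets the threshold ("Statistical significance level was accepted as p<0.05"). It plans mean±SD or median (min-max) as descriptive summaries. Between groups it plans one-way ANOVA followed by Tukey or Tamhane T2, or Kruskal-Wallis followed by Bonferroni-corrected Mann-Whitney tests. It mentions no estimated difference, confidence interval or equivalence margin.

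Demographic Findings prints mean ages and SDs for all four groups. Of H against SH it says: "It was determined that the mean age of the individuals was similar", with p=1,000.

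For IL-17E between groups, the results say that "there was no statistically significant difference between the groups in terms of both periodontal disease and smoking at any time", followed by p>0.05. The IL-17A section reports the between-group result in much the same way. Neither section prints a group summary, a difference or an interval.

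**The concern.** A p-value above 0.05 does not say how large a difference the data still allow. With 11 per group that range is wide. For IL-17A and IL-17E the whole between-group result is p>0.05, so a reader cannot judge whether a relevant effect of disease or smoking has been excluded or whether the study was too small to show it.

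The age statement is the one place where a non-significant test becomes a positive conclusion. It matters because H and SH together form the smoking contrast among healthy people. If their ages are taken as alike, a reader will not consider age when interpreting that contrast.

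**Working it through.** **1. Reproducing the printed age p-values.** Inputs from Demographic Findings: figures labelled Z of 18,000 (H v SP), 16,682 (H v P) and 3,682 (H v SH). Taken as differences in mean rank after a Kruskal-Wallis test with N=44 and 11 per group, ignoring ties, the standard error is √[N(N+1)/12 × (1/11 + 1/11)] = √[165 × 2/11] = √30 = 5.477. Four groups give six pairs, so Bonferroni multiplies by 6.

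| Pair | Rank difference / SE | Unadjusted p | × 6 | Printed p |
|---|---|---|---|---|
| H v SP | 18.000/5.477 = 3.286 | 0.00102 | 0.006 | 0.006 |
| H v P | 16.682/5.477 = 3.046 | 0.00232 | 0.014 | 0.014 |
| H v SH | 3.682/5.477 = 0.672 | 0.501 | 3.01, capped at 1 | 1.000 |

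The first two rows match the printed values, so this reading is sound. In the third row, the printed 1.000 is a capped Bonferroni value. The unadjusted p is about 0.50.

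**2. What the age data allow.** Inputs: SH 30.27 (SD 9.99) and H 26.36 (SD 4.20), n=11 each. The SDs differ, so a Welch interval is used.

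- Difference: 30.27 − 26.36 = 3.91 years.
- SE: √(9.99²/11 + 4.20²/11) = √(9.073 + 1.604) = 3.267, with 13.4 degrees of freedom and t = 2.153.
- 95% CI: 3.91 ± 2.153 × 3.267 = 3.91 ± 7.04, that is -3.1 to 10.9 years.

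As a standardised difference this is 3.91/√[(9.99² + 4.20²)/2] = 3.91/7.66 = 0.51 SD.

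**3. Precision of any pairwise mean difference.** With 11 v 11 and a common SD, the 95% half-width is t(0.975, 20 df) × √(2/11) = 2.086 × 0.426 = 0.89 SD. At the Bonferroni level for six pairs (0.05/6 = 0.0083) it is 1.25 SD.

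**4. Power of a single 11 v 11 pair.** The documents state no target difference, so the sizes below are assumptions. Powers are from the two-sided noncentral t with 20 df.

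| Assumed difference | Power at 0.05 | Power at 0.05/6 |
|---|---|---|
| 0.5 SD | 20% | 6% |
| 0.8 SD | 43% | 18% |
| 1.0 SD | 61% | 31% |

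The difference detectable with 80% power is 1.26 SD at 0.05 and 1.63 SD at 0.05/6. With Tukey, which the plan names for normal data with equal variances (40 error df, critical value 3.791/√2 = 2.68), it is 1.51 SD, and power at 1.0 SD is 38%.

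**The case against.** The strongest reply is that the documents mostly report tests correctly. Saying that a comparison was not statistically significant is accurate, and no section claims that any marker is equivalent between groups. The word similar is used once, for a demographic variable, and even without correction the p-value is 0.50, so the correction did not create the non-significance. Group summaries are planned, and age means and SDs are printed. All of this stands, and it limits the point to missing estimates and one unsupported word.

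Several stronger readings are tempting, but the documents do not support them.

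- *That every conclusion is pairwise and therefore unsupported by an ANOVA-based sample size.* Many results are omnibus or within-group. The IL-17A and IL-17E between-group nulls are most naturally omnibus, because pairwise tests follow only a significant Kruskal-Wallis result and no pairwise p-values are given. The pairwise power figures above do not describe those two results.
- *That the IL-17 markers yielded nothing but nulls.* IL-17A rose significantly within group P by day 30.
- *That 44 is shown to be too few.* With no effect size, SD or power stated, there is no target to contradict. Any effect size solved back from 11 per group would be the reviewer's number, not the sponsor's.
- *That low power undermines the significant periostin contrasts (SP v P, P v H).* It does not. They too would be more useful with estimates and intervals.
- *That 1.63 SD is the detectable difference.* It is the Bonferroni case; Tukey gives about 1.5 SD.

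**Conclusion.** The point holds as a gap in analysis and reporting. The plan provides no estimate or interval for any between-group contrast. At 11 per group, where a 95% interval extends about ±0.89 SD around a pairwise mean difference, a non-significant result cannot be told apart from one that could not have been detected.

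The age conclusion for H and SH is not supported as written. The data fit anything from H being about 3 years older to SH being about 11 years older. That does not show the ages differ; it shows only that similarity was not established.

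The age interval rests on the printed means and SDs and on approximate normality of the two means. The ±0.89 SD figure assumes a common SD and no multiplicity adjustment. No published test result changes.

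**What to change.** 1. In the Statistical analysis section, require a difference with 95% CI (mean difference, or Hodges-Lehmann where rank tests are used) for SP-SH, P-H, SP-P and SH-H for each marker at baseline, and for SP-P at days 15 and 30. Only SP-P is asked for at the later visits because the Treatment and Follow-up Protocol recalls only the periodontitis patients. State whether the intervals are adjusted for multiplicity.
2. In Demographic Findings, replace the word similar by the SH minus H age difference and its interval: 3.9 years, 95% CI -3.1 to 10.9 from the printed figures, or the Hodges-Lehmann equivalent from the individual ages.
3. Report the IL-17A and IL-17E between-group results with these intervals, so that they are not read as absence of an effect. The existing not-significant wording can stay. No equivalence claim should be added, since no margin is stated.
4. Do not rewrite the sample-size paragraph around a back-solved effect size.

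The cost is a short extra analysis of existing data and somewhat less favourable wording. No new patients or measurements are needed.

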### **Treatment and Follow-up Protocol**

Patients in the SH and H groups were advised to come for routine controls by not applying any periodontal treatment. However for patients in the SP and P groups, non-surgical periodontal treatment was applied as full mouth debridement protocol in a single session, after the GCF samples were collected from selected pockets.

The periodontitis patients were called again on the 15th and 30th days after the treatment. First of all, the GCF sampling process was repeated from the teeth whose GCF sample was collected before. Then, clinical examination parameters (PI, GI, BOP, PD and CAL) values were measured again and recorded.

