### **Sample Teeth Clinical Findings**

GCF was taken from the 5 deepest pockets measured before the treatment from the patients in the SP and P groups of the study groups before the treatment, on the 15th and 30th days after the treatment. GCF was taken from 5 randomly selected teeth with  $GI=0$   $PI=0$  and  $PD \leq 3$  from individuals in SH and H groups.

All clinical parameters (PI, GI, BOP, PD, CAL and GCF volume) of these selected teeth were analyzed statistically. There was a significant difference between the groups in all clinical parameters before treatment. The measurements of SP and P groups were higher than the healthy groups ( $p<0.05$ ).

There was a significant difference between the groups in terms of BOP, PD, CAL and GCF volumes on the 15th and 30th days after treatment.

There was no statistically significant difference between the periodontitis groups (SP-P) and healthy groups (SH-H) on the 0th, 15th and 30th days in terms of smoking ( $p>0.05$ ).

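### At days 15 and 30 the sampled sites are cleared of plaque before the Plaque Index is scored, whereas baseline plaque was scored before any sampling, so sample-tooth follow-up PI is biased downward by an unknown amount

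*Combined protocol and SAP*

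**What the plan says.** The opening section, Study Protocol and Statistical Analysis Plan, records PI, GI, BOP, PD and CAL at six sites of every tooth. It separates this examination from fluid collection at baseline: "the participants were asked to come for GCF sample and treatment 1 day after the clinical evaluations, since bleeding may occur during probing".

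The same section describes the preparation for each GCF sample: "Before sampling, the sites were isolated with cotton rolls, saliva and supragingival plaque were removed by cotton pellets, if present". For the periodontitis groups, "GCF samples were obtained from the 5 deepest pockets before the treatment, on the 15th and 30th days after the treatment". The healthy groups (SH and H) were sampled at teeth chosen to have PI = 0 and GI = 0.

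Treatment and Follow-up Protocol sets the order at the recall visits of the SP and P patients: "First of all, the GCF sampling process was repeated from the teeth whose GCF sample was collected before". The next sentence reads: "Then, clinical examination parameters (PI, GI, BOP, PD and CAL) values were measured again and recorded".

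Sample Teeth Clinical Findings makes PI of these teeth an analysed variable: "All clinical parameters (PI, GI, BOP, PD, CAL and GCF volume) of these selected teeth were analyzed statistically". It reports between-group differences "in terms of BOP, PD, CAL and GCF volumes on the 15th and 30th days after treatment". PI and GI are not in that list. Full Mouth Clinical Findings reports a significant within-group fall in every index, PI included, in both SP and P.

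**The concern.** A change from baseline is interpretable only if the measurement is taken under the same conditions each time. Here the sampling step removes the very thing that PI measures, and it comes after PI at baseline but before PI at both follow-up visits. Plaque that the patient brought to the visit is removed from the sampled site before it can be counted.

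The error has one direction. It can only lower follow-up PI, and it adds to any true fall after treatment. More patients or a different test would not remove it. The comparison with the healthy groups is also affected: their teeth were chosen with PI = 0, so wiping the treated sites moves SP and P towards them. What is at stake is the use of sample-tooth PI as evidence of treatment response or plaque control at the sites whose biomarkers are interpreted.

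**Working it through.** **Order of steps, side by side**

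| Visit | First | Second | State of plaque when PI is scored |
|---|---|---|---|
| Baseline | PI and other indices | GCF sampling with plaque removal, one day later | Not disturbed by sampling |
| Day 15 | GCF sampling with plaque removal | PI and other indices | Sampled site already wiped |
| Day 30 | GCF sampling with plaque removal | PI and other indices | Sampled site already wiped |

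The recall visits repeat the sampling process, and the described process includes the wipe. Nothing in the documents says that PI was scored before the wipe at follow-up, or that sampled sites were left out of PI.

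**Possible size.** The plan gives no figure to reproduce. It does not report PI values, how many of a tooth's sites the cotton pellet covered, or how complete the removal was. The following is therefore a range under stated assumptions.

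Inputs:
- Scored sites per tooth: 6 (opening section).
- Sampled pockets per SP or P patient: 5 (opening section).
- Assumed: plaque spread evenly over sites; 28 teeth; the five pockets on five different teeth.

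Sample teeth: proportional fall in mean PI = (w / 6) × r, where w is the number of sites wiped per tooth and r is the fraction of the plaque score removed.
- w = 1, r = 1: 1/6 = 17%. With r = 0.5: 8%.
- w = 3, r = 1: 3/6 = 50%. With r = 0.5: 25%.

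Full mouth: proportional fall = (5 × w × r) / (6 × teeth).
- w = 1, r = 1, 28 teeth: 5/168 = 3.0%. With 20 teeth: 5/120 = 4.2%.
- w = 3, r = 1, 28 teeth: 15/168 = 8.9%.

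The text speaks of cleaning the sites, so w = 1 is the closest reading and w = 3 (one whole aspect of the tooth) is a wider one. Where a sampled site carried no plaque, the fall at that site is zero.

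**The case against.** The strongest reply is that a possible bias is not a demonstrated one. The wipe is confined to the sites and applies only if plaque is present, and the visits come 15 and 30 days after full-mouth debridement, when there may be little to remove. This stands as a limit on size. It does not restore comparability, because the amount removed was not recorded.

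A second reply is that sampling must come before probing, to keep blood off the strips. The plan gives that reason for its baseline order, and it is sound. It justifies probing last; it does not require plaque to be scored after the wipe. It does matter for the fix, because the plan lists PI among the indices measured with the periodontal probe.

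A third reply is that little depends on this variable. The within-group PI decrease is reported for the full mouth, where the site-only effect is about 3%. No within-group fall is reported for the sample teeth. SP and P had the same follow-up procedure, so no directional bias in the comparison between them is established. This stands, and it limits the importance of the point.

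Three stronger readings are tempting, and the documents do not support them:
- A reader might infer that the wipe explains why PI is missing from the list of differences at days 15 and 30. Treatment response explains it as well. A fall of 17% or 50% would not by itself bring a plaque-bearing tooth to zero. GI is missing from the list too, and wiping plaque is not shown to change GI.
- A reader might infer that follow-up PI could be zero whatever plaque was present. That needs PI to be taken only at the sampled site and the wipe to be complete. The plan scores six sites per tooth and analyses the selected teeth.
- A reader might infer that a strip left in the sulcus for 30 seconds also distorts GI and BOP. Nothing in the documents says so; the plan attributes bleeding to probing.

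**Conclusion.** The point holds for PI. As written, the plan scores PI before plaque removal at baseline and after it at days 15 and 30, on the same teeth, and it analyses the result. Follow-up PI at sampled sites that carried plaque is biased downward relative to baseline in SP and P.

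The size cannot be determined from the documents. With even plaque and complete removal, it is about 17% of sample-tooth mean PI for one wiped site and 50% for three. For full-mouth PI it is about 3% if only the sampled sites are wiped and 28 teeth are present. There is no ground here to say that the reported full-mouth PI decrease would be overturned.

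The absence of PI from the day-15 and day-30 differences is compatible with the artefact and with treatment response, and the design cannot separate them. PD, CAL and the periostin, IL-17A and IL-17E results are not shown to be affected, and no effect on GI or BOP is shown. The order of steps is certain; the amount of bias is not.

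**What to change.** In Treatment and Follow-up Protocol, change the order within the recall visit: score PI on the teeth to be sampled before isolation and plaque removal, without entering the sulcus; then take GCF; then carry out the probing measurements. This needs no extra visit or procedure. The cost is care in execution: plaque scoring must not provoke bleeding that would contaminate the strips.

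The results are already in the document, so that change helps only future use of the protocol. For the collected data:
- State whether PI at days 15 and 30 was in fact scored before the cotton-pellet step. If it was, say so, and the point is closed.
- If it was not, report sample-tooth PI at days 15 and 30 as not comparable with baseline or with the healthy teeth selected at PI = 0.
- Add a sensitivity analysis of full-mouth PI that leaves out the sampled sites at days 0, 15 and 30 alike. This relies on site-level records that identify the sampled sites. If the wipe is known to have covered neighbouring sites, leave those out too. Leaving out whole teeth is not advised as the default: it assumes one sampled pocket per tooth, which the plan does not state for SP and P, and it removes the teeth with the deepest pockets.

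The cost is a re-run of one variable and the loss of sample-tooth PI change as a result.
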